## **7.2.2 Post-Procedure Monitoring**

We will monitor patients for up to 12 months via chart review and patient phone calls. Targeted adverse events will be recorded if reported/found at each study follow-up visit.

If three unexpected adverse events occur, then we will put the study on hold and discuss the circumstances associated with the adverse events with the EP group (including the Chief of Cardiology and Chief of Electrophysiology), the anesthesiologists that were present during those cases, and the DSMB. At that time, alternatives to the study design and the possibility of discontinuing the study will be discussed.

## **8.0 PROTOCOL DEVIATIONS**

The Principal Investigator is required to adhere to the study protocol, the signed Principal Investigator's Agreement, applicable federal (national) or state/local, laws and regulations, and any conditions required by the IRB or applicable regulatory authorities.

A protocol deviation is used to describe situations in which the clinical protocol was not followed. All deviations from the study protocol must be reported on the Protocol Deviation CRF to the UCSF CC, as soon as possible, but no later than 10 working days of notification of the event. In addition, all deviations must be reported to the local IRB per the IRB's reporting requirements. Protocol deviations will also be reported to the DSMB.

## **9.0 QUALITY ASSURANCE AND DATA MANAGEMENT**

### **9.1 Clinical Site Investigator and Coordinator Training**

Each investigator and coordinator will be trained on the study protocol and procedures to ensure accurate and consistent study methods are used study-wide and throughout the entire study duration. Trainings will include review of the protocol, operations manual, CRFs, event reporting, and data management procedures. If any protocol amendments occur during the study, research team trainings will be scheduled as needed.

### **9.2 Data Handling and Confidentiality**

Information about study participants will be kept confidential and managed according to the requirements of the Health Insurance Portability and Accountability Act of 1996 (HIPAA). Those regulations require a signed patient authorization informing the patient of the following:

- What protected health information (PHI) will be collected from patients in this study
- Who will have access to that information and why
- Who will use or disclose that information
- The rights of a research patient to revoke their authorization for use of their PHI.

In the event that a participant revokes authorization to collect or use PHI, the Principal Investigator, by regulation, retains the ability to use all information collected prior to the revocation of participant authorization. For participants that have revoked authorization to collect or use PHI, attempts should be made to obtain permission to collect at least vital status (i.e., that the participant is alive) at the end of their scheduled study follow-up.

### **9.3 Source Documents**

Study files will be kept in a secure location. Participant files should include archives of completed CRFs and source documents. The study case report forms (CRFs) are the primary data collection instrument for the study and are considered source documents. Source data also include original records of clinical findings, observations, or study measurement results (e.g., hospital records, clinical and office charts, laboratory notes, dispensing records, recorded data from automated instruments, and patient files).

### **9.4 Data Collection and Management**

A member of the research team will enter data from each CRF into the study REDCap database. The study data is subjected to checks for completeness, consistency and validity. Upon completion of data collection and all data cleaning efforts have been performed, the database will be locked and analyses will commence.

## **10.0 STATISTICAL METHODS**

Demographic and baseline characteristics will be described using mean with standard deviation, median and interquartile range, or proportions, where appropriate. The change in AERP and conduction times will be compared within cohorts using paired t-tests (if the outcome is not normally distributed, the Wilcoxon sign rank test will be used), and the changes in those values will be compared by treatment assignment (ethanol versus placebo) using t-tests or Wilcoxon rank sum tests as appropriate. The proportion with inducible AF will be compared by treatment assignment using the chi-squared test, and a logistic regression model will be utilized to adjust for potential confounders that are not addressed by randomization. Full details will be outlined in the Statistical Analysis Plan.

The Primary Analyses will be conducted in the “Analysis Population”, which includes all participants who are (1) randomized and (2) have received the study infusion. Secondary analyses will be conducted in the full “Randomized Population”, which includes all participants who have been randomized, whether or not they received the study infusion

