## **2.0 INVESTIGATION PLAN**

### **2.1 Study Design**

This study is a randomized single-center single-blinded placebo controlled trial of patients age 21-90 with paroxysmal atrial fibrillation. This study will be conducted at University of California, San Francisco (UCSF) Medical Center. One hundred patients will be enrolled and will receive the study infusion (alcohol or placebo infusion).

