### 3.5 Post-Infusion EP Study

As soon as the blood alcohol content reaches a steady state of  $0.080\% \pm 0.002\%$ , a one-minute premature atrial contraction (PAC) count will be conducted. AERP measurements will then be taken at the following bipoles: CS proximal, CS distal, high right atrium (crista terminalis catheter), left upper pulmonary vein, and right upper pulmonary vein. The AERP will be obtained by an incremental technique using a 600 ms drive cycle length for 8 beats (S1) at twice pacing threshold with incremental steps for the atrial extrastimuli (S2). The first drive train at each location should begin with an atrial extrastimuli (S2) of 140 ms, which is not expected to result in atrial capture. Once the first atrial capture is achieved, the S2 will be decreased by 5 ms. AERP will be defined as the longest S1-S2 interval that fails to result in atrial capture. (See Operations Manual for details)

Following the PAC count and AERP measurements, a phenylephrine infusion will be started prior to the initiation of the isoproterenol infusion to maintain a mean arterial pressure of  $>60$  mmHg. Isoproterenol hydrochloride will then be infused at the following rates for 2 minutes each: 3 mcg/min, 6 mcg/min, 12 mcg/min, and 20 mcg/min. If AF or another arrhythmia initiates at any point during the isoproterenol infusion and is sustained over 30 seconds, the isoproterenol infusion will be stopped, the rhythm documented, and the study terminated.

If neither AF nor another arrhythmia lasting over 30 seconds occurs after 2 minutes of 20 mcg/min isoproterenol infusion, the isoproterenol infusion will be stopped. Once the heart rate falls below 100 bpm, up to 3 bursts of rapid atrial pacing will be performed from the CS proximal bipole. If AF or another arrhythmia initiates at any point during the burst pacing and is sustained over 30 seconds, the study will be terminated and the rhythm documented.

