### **4.1 Untreated Randomized Participants**

After randomization, if an exclusionary criterion is identified prior to or at the start of the study procedure, the participant will not undergo the study infusion procedure. Randomized participants may be early terminated, prior to commencing the study procedure, and will not receive the study infusion if any of the following study exclusions are identified:

- Participants who present in AF sustained >1 week
- If a participant does not present in sinus rhythm at the procedure, but he or she has proven to be in sinus rhythm at the enrollment visit, it is up to the attending whether or not to cardiovert the patient and proceed with study protocol. If the participant is to be cardioverted, the cardioversion should take place prior to transseptal puncture and following right catheter placement to minimize potential effects on AERP and conduction times. If a second AF episode initiates and is sustained over 2 minutes prior to initiation of study procedure, the study will be aborted.

These participants will be considered as “Untreated Participants”. Unrandomized participants who do not commence/receive the study infusion will not continue in follow-up and will not be included in analyses.

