### 5.1 Screening for Inclusion/Exclusion Criteria & Randomization

Each potential participant's medical record will be reviewed for available inclusion and exclusion criteria data. After the participant provides informed consent, his or her medical history and additional demographic data will be obtained. Initial screening will occur at least 1 day prior to the patient's scheduled ablation procedure.

The pharmacy that prepares the ethanol/placebo infusion bags requires notification of the treatment assignment 1 business day prior to administration in order to prepare the infusion bag. Therefore, participants must be consented and randomized at least 1 day prior to the scheduled procedure.

Baseline measures will include:

- Inclusion/Exclusion criteria assessment
- Demographics and medical history
- World Health Organization AUDIT questionnaire
- CARDIA alcohol use questionnaire (shortened version)
- Vital signs
- Infusion, procedure, BrAC, and EP study measurements
- Arrhythmia episodes pre/during/post-procedure
- Adverse event assessment

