The HOLIDAY (HOw ALcohol InDuces Atrial TachYarrhythmias) Study

NCT Number: NCT01996943

Document Type: Statistical Analysis Plan

Document Date: 12/7/2020

HOLIDAY Study Statistical Analysis

Normally distributed continuous variables are presented as means \pm SD and were compared using t-tests, and continuous variables with skewed distributions are presented as medians and interquartile ranges (IQR) and were compared using Wilcoxon rank sum or signed rank tests as appropriate. Categorical variables were compared using chi squared and Fisher's exact tests. The proportion of atrial effective refractory periods that decreased with the infusion, the proportion of conduction times that decreased with the infusion, and the continuous change in each individual atrial effective refractory period and conduction time were assessed. Linear mixed models (LMMs) to estimate average and site-specific effects on pre- to post-infusion changes in AERP and conduction times were performed, with site and baseline values modeled as fixed effects and participants as random effects; analyses were repeated after adjusting for covariates statistically significantly different between alcohol and placebo groups. Heterogeneous relationships between pulmonary vein and non-pulmonary vein sites were assessed using formal tests for interaction. In addition, given evidence of potential effect modification by biological sex (19), tests for interaction by sex on the relationships between randomization assignment and outcomes were performed. Based on a review of repeat AERP measurements in 30 AF patients at 600 ms drive cycle length prior to the trial (yielding an average ERP of 230 ms \pm 20 ms), we estimated that 22 patients in each group would provide 90% power to detect a statistically significant one standard deviation difference in the overall AERP using a single interim analysis for efficacy (assessed by an independent Data Safety Monitoring Board) and an overall two-sided $\alpha = 0.05$. We based power calculations for the secondary analysis on 25 paroxysmal AF patients in whom AF induction occurred in 20%; we therefore estimated that 50 patients in each group would provide 84% power to detect a 30% increase in AF induction (20% versus 50%) with ethanol, again using a single interim analysis for efficacy and an overall two-sided $\alpha = 0.05$. Analyses were conducted using Stata version 16 (College Station, Texas). Two-sided p values < 0.05 were considered statistically significant.

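### Is the AF-induction comparison left without a usable denominator, because the plan does not say how randomized but untested patients count?

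*Protocol*

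**What the plan says.** Protocol Section 10.0 compares the proportion with inducible AF between arms by chi-squared test, without naming a denominator in that sentence. It then defines two populations. The Analysis Population, used for the primary analyses, is "all participants who are (1) randomized and (2) have received the study infusion". The Randomized Population, used for secondary analyses, is "all participants who have been randomized, whether or not they received the study infusion".

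Protocol Section 4.1 is headed as concerning untreated randomized participants, yet its last sentence reads "Unrandomized participants who do not commence/receive the study infusion will not continue in follow-up and will not be included in analyses".

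Induction testing comes last in the procedure. Section 3.5 says "Following the PAC count and AERP measurements, a phenylephrine infusion will be started prior to the initiation of the isoproterenol infusion", and burst pacing follows only if isoproterenol produces no sustained arrhythmia. Randomization comes earlier, since "participants must be consented and randomized at least 1 day prior to the scheduled procedure" (Section 5.1). Sections 4.2 and 4.2.1 keep patients in follow-up when the infusion began but the procedure was not completed.

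On size, Section 2.1 says "One hundred patients will be enrolled and will receive the study infusion". The SAP says "We based power calculations for the secondary analysis on 25 paroxysmal AF patients in whom AF induction occurred in 20" percent, and that "50 patients in each group would provide 84% power to detect a 30% increase in AF induction (20% versus 50%) with ethanol". It names no analysis population and no rule for a missing induction result.

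**The concern.** Two kinds of randomized patient can lack an induction result: those never infused, and those infused but stopped before the test. Three denominators are then conceivable (tested, infused, randomized).

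The protocol's word for the second set of analyses and the SAP's word for the induction outcome are both some form of secondary. Joined together, they seem to place this comparison in all randomized patients, including people who could not have been tested. Section 4.1, if its first word is a misprint, says the opposite.

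For infused patients without a test, the missing result could carry information. A second sustained AF episode ends the study procedure (Section 4.2.1), and Aim 2 expects more AF with ethanol. The anesthesiologist, who may stop the infusion, is unblinded (Section 7.2.1). In a 50-patient arm, each such patient moves that arm's proportion by 1/50 = 2 points, depending on whether the patient is scored induced or not induced. At stake is the size, and possibly the significance, of the Aim 2 result.

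**Working it through.** **Inputs.** The SAP gives 50 per group, 20% versus 50%, two-sided alpha 0.05 and one interim look with no stated boundary. Protocol Section 2.1 gives 100 infused patients. The numbers not infused or not tested are not given, so all such counts below are assumptions.

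**The plan's own figure.** Pooled-variance power is Φ[(0.30 − z·√(2·0.35·0.65/50)) / √((0.20·0.80 + 0.50·0.50)/50)].
- z = 1.960 (alpha 0.05): (0.30 − 0.187)/0.0906 = 1.248, power 89.4%.
- The same with a continuity correction (0.30 − 1/50 in the numerator): 1.027, power 84.8%.
- Uncorrected at 0.0294, an assumed Pocock level for two looks: 1.019, power 84.6%.

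The stated 84% is therefore reproduced to within a point by either of two standard routes, with 50 per group all contributing a result. The calculation rests on infused and tested patients.

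**Reading the passages together.** Section 10.0 pairs primary analyses in infused patients with secondary analyses in all randomized patients. The plain reading is a main analysis and a supportive repeat. The protocol does not rank induction as secondary; Section 2.5 lists it as Aim 2. Only a power sentence in the SAP uses that word. Section 2.1 and the SAP's 50 per group both fit an infused denominator.

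**Patients not infused.** Start from 25/50 versus 10/50. Pearson chi-squared = 100·(25·40 − 10·25)²/(50·50·35·65) = 9.89, p=0.0017. Add u per arm, all scored non-inducible:

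| u | Ethanol | Placebo | Difference | p | Exact power |
|---|---|---|---|---|---|
| 0 | 50.0% | 20.0% | 30.0 | 0.0017 | 89.5% |
| 5 | 45.5% | 18.2% | 27.3 | 0.0021 | 89.0% |
| 10 | 41.7% | 16.7% | 25.0 | 0.0026 | 88.5% |

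If they are left out, the Randomized Population result equals the infused result for this outcome.

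**Infused but untested.** Take a severe case: k stops, all on ethanol, all among the 25 expected to be inducible. Scoring them AF-positive leaves 30 points and p=0.0017 throughout.

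| k | Left out: (25−k)/(50−k) vs 10/50 | Non-inducible: (25−k)/50 vs 10/50 |
|---|---|---|
| 2 | 27.9 points, p=0.0035 | 26 points, p=0.0057 |
| 5 | 24.4 points, p=0.0105 | 20 points, p=0.0291 |
| 6 | 23.2 points, p=0.0152 | 18 points, p=0.0473 (Fisher 0.077) |
| 7 | 21.9 points, p=0.0219 | 16 points, p=0.0748 |
| 9 | 19.0 points, p=0.0456 | 12 points, p=0.1713 |

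Significance at 0.05 is lost from 7 patients by chi-squared (6 by Fisher's exact test), and only under non-inducible scoring. For stops caused by recurrent AF, that would mean recording patients with two sustained AF episodes as not susceptible to AF. Between AF-positive and left out, the chi-squared conclusion is the same up to 9 such patients.

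**The case for a change.** The strongest opposing case is that the documents do leave this unwritten. Section 10.0 defers full details to the SAP, and the SAP supplies neither a population nor a scoring rule. The Operations Manual, which is not available here, is cited for early-termination procedures and measurement details, not for analysis sets. Section 4.1, with its probable slip, disagrees with the Randomized Population however the word secondary is read.

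Unequal loss also matters more than equal loss. Suppose 10% of ethanol patients and no placebo patients are untested, with 50% and 20% inducible among the tested. The comparison is then 45% versus 20% if they are scored non-inducible (power 76.9%) and 55% versus 20% if scored AF-positive (96.2%). With tested patients only, power is 87.8%. That spread is not trivial.

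What stands is that the wording is untidy and the scoring of an infused, untested patient is not stated. What does not follow is that the plan yields a wrong result. No passage proposes counting a never-tested person as non-inducible. No frequency of such stops is given, and stopping an infusion under Section 7.2.1 does not by itself mean the induction test is skipped. The spread depends on one-sided loss that the documents give no figure to support.

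**Conclusion.** No change is called for. In Section 4.1, the printed first word does not fit the section heading or the sentence before it, so it is a clerical slip that a reader can see through. The choice of denominator is a gap that analysts fill sensibly: infused patients for the main comparison, as the Analysis Population and the sample size both imply, with the few untested patients visible in the participant flow. The Study Treatment form records whether the procedure was completed as intended (Section 3.6), and arrhythmia episodes are collected (Section 5.1).

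A newly written rule would gain little. The SAP is dated 12/7/2020 and written in the past tense, so a rule added now might not count as pre-specified, and nothing shows one coding to be better than another for every kind of stop.

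On the assumptions above, 10 uninfused patients per arm move the estimate by 5 points and p from 0.0017 to 0.0026. Loss of chi-squared significance needs 7 of 50 ethanol patients (14%) stopped with none on placebo, all inducible and all scored non-inducible. These figures assume the planned 50% versus 20%, 50 infused per arm and the full 0.05 level; the interim boundary is not stated. The judgement would be different only if many patients, mostly in one arm, were infused but never tested.

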## **11.0 ETHICAL CONSIDERATIONS**

This study is to be conducted according to US and international standards of Good Clinical Practice (FDA Title 21 part 812 and International Conference on Harmonization guidelines), applicable government regulations and Institutional research policies and procedures.

### **11.1 Institutional Review Board (IRB) Approval**

This protocol and any amendments will be submitted to a properly constituted IRB.

### **11.2 Informed Consent**

Study personnel must explain to each participant (NOTE: consent by proxy is not allowed for this study) the nature of the study, its purpose, the procedures involved, the expected duration, the potential risks and benefits involved and any discomfort it may entail. Each participant must be informed that participation in the study is voluntary and that he/she may withdraw from the study at any time and that withdrawal of consent will not affect his/her subsequent medical treatment or relationship with the treating physician. Patients will have to demonstrate adequate reasoning faculties and will have to demonstrate understanding of the implications, risks, benefits and alternatives to participating in the study before consent is obtained. This will include asking potential participants questions to assure they understand the ramifications of participation.

This informed consent will be given by means of a standard written statement, written in non-technical language. The subject should read and consider the statement before signing and dating it, and should be given a copy of the signed document. If the participant cannot read or sign the document, oral presentation may be made or signature given by the participant's legally appointed representative, if witnessed by a person not involved in the study, mentioning that the participant could not read or sign the documents. No participant will receive a study infusion before his/her informed consent has been obtained.

### **11.3 Declaration of Helsinki**

The investigator must conduct the trial in accordance with the Declaration of Helsinki.

The HOLIDAY (HOw ALcohol InDuces Atrial TachYarrhythmias) Study

NCT Number: NCT01996943

Document Type: Statistical Analysis Plan

Document Date: 12/7/2020

HOLIDAY Study Statistical Analysis

Normally distributed continuous variables are presented as means \pm SD and were compared using t-tests, and continuous variables with skewed distributions are presented as medians and interquartile ranges (IQR) and were compared using Wilcoxon rank sum or signed rank tests as appropriate. Categorical variables were compared using chi squared and Fisher's exact tests. The proportion of atrial effective refractory periods that decreased with the infusion, the proportion of conduction times that decreased with the infusion, and the continuous change in each individual atrial effective refractory period and conduction time were assessed. Linear mixed models (LMMs) to estimate average and site-specific effects on pre- to post-infusion changes in AERP and conduction times were performed, with site and baseline values modeled as fixed effects and participants as random effects; analyses were repeated after adjusting for covariates statistically significantly different between alcohol and placebo groups. Heterogeneous relationships between pulmonary vein and non-pulmonary vein sites were assessed using formal tests for interaction. In addition, given evidence of potential effect modification by biological sex (19), tests for interaction by sex on the relationships between randomization assignment and outcomes were performed. Based on a review of repeat AERP measurements in 30 AF patients at 600 ms drive cycle length prior to the trial (yielding an average ERP of 230 ms \pm 20 ms), we estimated that 22 patients in each group would provide 90% power to detect a statistically significant one standard deviation difference in the overall AERP using a single interim analysis for efficacy (assessed by an independent Data Safety Monitoring Board) and an overall two-sided $\alpha = 0.05$. We based power calculations for the secondary analysis on 25 paroxysmal AF patients in whom AF induction occurred in 20%; we therefore estimated that 50 patients in each group would provide 84% power to detect a 30% increase in AF induction (20% versus 50%) with ethanol, again using a single interim analysis for efficacy and an overall two-sided $\alpha = 0.05$. Analyses were conducted using Stata version 16 (College Station, Texas). Two-sided p values < 0.05 were considered statistically significant.

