### **2.2 Randomization and Treatment Groups**

Participants will be allocated (1:1) to a study assignment, using alternating blocked randomization (in blocks of five). Participants will be assigned to either the Ethanol Infusion group or to the Placebo Infusion group.

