### **3.2 Catheter Placement**

Following the initiation of sedation, intra-cardiac multipolar electrocatheters will be placed in the following positions under fluoroscopic guidance: decapolar catheter in the coronary sinus (CS), decapolar catheter along the crista terminalis, quadripolar catheter along the medial tricuspid annulus at the position of the His bundle, duodecapolar circular catheter in the left upper pulmonary vein, and quadripolar ablation catheter in the right upper pulmonary vein. If the ablation procedure were a cryoballoon PVI, four, instead of five, catheters will be used: decapolar catheter in the coronary sinus (CS), decapolar catheter along the crista terminalis, quadripolar catheter along the medial tricuspid annulus at the position of the His bundle, and cryoballoon catheter in the left upper pulmonary vein. (See Operations Manual for details)

Catheter repositioning should be avoided to prevent disrupting post-procedure conduction time measurements. Prior to transseptal access, the alcohol or placebo solution will be connected to minimize left atrial time.

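### Does the missing unit and test for the proportions of AERPs and conduction times that decreased make the SAP's analysis invalid?

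*SAP*

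**What the plan says.** The SAP is one paragraph under the heading HOLIDAY Study Statistical Analysis. It lists "The proportion of atrial effective refractory periods that decreased with the infusion, the proportion of conduction times that decreased with the infusion", together with the continuous change at each individual site, as quantities that were assessed. It gives no denominator and no test for the two proportions.

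The SAP's general rules are these:

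- For categorical data: "Categorical variables were compared using chi squared and Fisher's exact tests".
- For continuous data: t-tests when normally distributed; skewed variables "were compared using Wilcoxon rank sum or signed rank tests as appropriate".
- For pre- to post-infusion changes in AERP and conduction time: linear mixed models "with site and baseline values modeled as fixed effects and participants as random effects", giving average and site-specific effects.
- For differences between kinds of site: "Heterogeneous relationships between pulmonary vein and non-pulmonary vein sites were assessed using formal tests for interaction".

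In the protocol, section 2.1 states that "One hundred patients will be enrolled and will receive the study infusion", and section 2.2 that "Participants will be allocated (1:1) to a study assignment". Sections 3.3 and 3.5 measure AERP at five bipoles before and after infusion. Section 3.2 says that in cryoballoon cases "four, instead of five, catheters will be used". Section 10.0 compares changes in AERP and conduction times, and uses chi-squared only for inducible AF, which is one result per patient. It has no outcome of the proportion-decreased kind and leaves full details to the SAP.

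**The concern.** Read literally, the SAP counts refractory periods and conduction times, not patients. The nearest rule for a proportion is ordinary chi-squared or Fisher, and the participant random effect is stated only for the continuous changes. The patient is the unit randomised, and all of a patient's sites fall in one arm. A patient's before/after differences also come from the same two EP studies, so some positive correlation is plausible.

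A reader could therefore infer that about 250 sites per arm (50 patients times five) were entered as independent observations. If so, the p-value for more AERPs shortening under alcohol would be too small and its confidence interval too narrow. With p below 0.05 declared significant, a chance imbalance driven by a few patients could be reported as an effect on the atrium.

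**Working it through.** **1. The plan's own figures.** They are at patient level and reproduce. For a one-SD difference, two-sided 5% and 90% power, n per group = 2 × (1.960 + 1.282)² / 1² = 21.0, rounded up to 22; the t-test power at 22 is 0.900. For AF induction of 20% versus 50% with 50 per group, power is 0.848 with continuity correction and 0.853 by exact Fisher, against the stated 84%. Neither calculation uses the proportion of sites that decreased.

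**2. Inputs for the pooled reading.** From the documents: 50 patients per arm (100 patients, 1:1), five AERP sites, two-sided 5%. Assumed, because the documents do not say: four sites in cryoballoon cases; a mean chance of decreasing of 0.4, either equal at all sites or evenly spread from 0.2 to 0.6; normal latent changes with one common correlation ρ between any two sites, taken from 0.1 to 0.5.

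**3. Formulas.** With m sites, chances pᵢ and mean p̄:

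- Design effect DE = (sum of all site variances and covariances) / (m × p̄ × (1 − p̄)).
- Actual error of the pooled chi-squared test = 2 × (1 − Φ(1.96 / √DE)).

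Example: five equal sites, ρ = 0.1. The variances sum to 5 × 0.24 = 1.20 and the covariances to 0.30. DE = 1.50 / 1.20 = 1.25, and the error is 2 × (1 − Φ(1.96 / 1.118)) = 8.0%.

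**4. Results for pooled chi-squared.**

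| Sites | DE at ρ = 0.1, 0.3, 0.5 | Actual error |
|---|---|---|
| Five, equal | 1.25, 1.76, 2.32 | 8.0%, 14.0%, 19.8% |
| Five, differing | 1.13, 1.57, 2.03 | 6.6%, 11.8%, 16.9% |
| Four, equal | 1.19, 1.57, 1.99 | 7.2%, 11.8%, 16.5% |
| Four, differing | 1.07, 1.39, 1.72 | 5.8%, 9.6%, 13.5% |

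When sites differ in their chance of decreasing, pooling is slightly conservative at ρ = 0: with five sites DE is 1.10 / 1.20 = 0.92 and the error 4.1%. Inflation starts only above ρ of about 0.04 (five sites) or 0.06 (four). Fisher on pooled sites is milder; in simulation it gave 4.3% for four differing sites at ρ = 0.1. If the correlation is set on the yes/no scale instead, DE = 1 + (m − 1) × ICC, and five sites at ICC 0.1, 0.3 and 0.5 give 9.8%, 18.6% and 25.8%. These are larger because a latent ρ of 0.1 to 0.5 corresponds to only about 0.06 to 0.33 on that scale.

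**5. The other readings.**

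- *Each patient's own fraction of decreased sites.* This is one number per patient, so the SAP's t-test or Wilcoxon rule applies. Simulated error was 4.7% to 5.4% (t-test) and 4.3% to 5.7% (Wilcoxon).
- *One site at a time.* Each patient contributes one yes/no value, so chi-squared or Fisher has no clustering problem. The same SAP sentence goes on to the change at each individual site, and the next names site-specific effects, which supports this reading.
- *Description only.* No test is attached, so there is no error rate to inflate.

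**6. Conduction times.** No figure can be given, because neither document states how many each patient contributes.

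**The case for a change.** The strongest case for a change is that the SAP is where this detail belongs, since protocol section 10.0 defers to it, and that the text does not settle which reading is meant. The grammar leans towards counting sites. The proportions come first among the AERP and conduction assessments, and an explicit participant random effect for continuous change makes its absence for the yes/no version conspicuous. One or two sentences would close the gap.

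Much of that stands. The unit and test are missing, and the pooled analysis would be wrong under any appreciable correlation. What does not follow is that the plan prescribes it. Going from the text to an inflated p-value takes three steps that the documents do not supply: that these proportions were tested, that sites were pooled, and that the correlation was large enough to matter. The mixed model cuts the other way as well, because it shows that the analysts had recognised the repeated sites per patient. A rule requiring a patient-clustered method would also shut out the site-by-site comparison, which is valid as it is.

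**Conclusion.** The concern does not call for a change. It identifies an unstated unit and test, not a stated rule that gives a wrong answer. An actual error of 5.8% to 19.8% for pooled chi-squared is a fair measure of what careless pooling would cost, but it rests on assumed correlations of 0.1 to 0.5, an assumed mean chance of 0.4 and a pooled test that the SAP never specifies. On each of the other three readings there is no clustering inflation.

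Little hangs on it in any case. Inference on AERP and conduction time is carried by mixed models with participant random effects, the protocol has no outcome of this kind, and neither sample-size calculation uses it. The SAP is also written in the past tense, so what remains is a matter of reporting: whoever presents these proportions should say whether they count patients or sites.
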